8 STUDY ASSESSMENTS AND PROCEDURES

8.1 EFFICACY ASSESSMENTS

Primary Objective

To test the efficacy of two interventions (Clinical Decision Support with and without Patient Education), compared to treatment-as-usual to decrease opioid prescribing for dental extractions.

Data source: HealthPartners electronic health record

Procedures:

1. Gather extraction procedure records performed prior to and post CDS implementation
2. Gather opioid medication orders placed within 7 days of extraction procedure
3. Retrieve patient and provider descriptive data

Secondary Objectives

To test the efficacy of two interventions (Clinical Decision Support with and without Patient Education), compared to treatment-as-usual to increase exclusive non-opioid pain management for dental extractions.

Data source: HealthPartners electronic health record

Procedures:

1. Gather extraction procedure records performed prior to and post CDS implementation
2. Gather non-opioid medication recommendations given within 7 days of extraction procedure
3. Gather patient and provider descriptive data

To compare the degree to which each of the 3 study arms (Clinical Decision Support with and without Patient Education, and treatment-as-usual), facilitates shared provider and patient decision-making concerning pain management options for dental extractions.

Data source: Telephone administered patient survey responses

Procedures:

1. CESR staff will administer the survey by telephone
2. CESR staff will input patient responses into RedCap
3. Data will be exported and provided to the statistician

To explore whether the study interventions lead to differences in patient experiences of post-extraction pain. Data source: Patient survey

Procedures:

1. CESR staff will administer the survey by telephone
2. CESR staff will input patient responses into RedCap
3. Data will be exported and provided to the statistician

8.2 SAFETY AND OTHER ASSESSMENTS

The study does not include objectives or endpoints concerning safety. However, the monitoring activities described below will be conducted to assess possible harm.

Identify whether the CDS inappropriately fires or inappropriately offers considerations

Data source: Provider report to alert study team about potential issues or concerns

Procedures:

1. Providers randomized to an intervention arm will be offered training.

2. They will be instructed to notify the study team when clinical judgement differs from the CDS
3. Notification options: (a) Contact Co-Investigator [name] or PI [name]; (b) select a "feedback" button contained within the CDS

Identify potential adverse events

Data source: HealthPartners electronic health record

Procedures:

1. Gather hospitalizations, emergency department visits, observational bed, and subsequent opioid prescribing made within 3 days post-extraction procedure

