Potential risks to patient participants are considered minimal. For patients in all study arms, there is a potential breach of privacy of individually identifying study data. To minimize this risk, no individually identifying patient information will be made available in publication or dissemination efforts. Results that are shared will be in aggregate form.

For patients whose providers are exposed to the CDS, there are several additional potential risks. First, the CDS may not display all relevant clinical information about the patient, as the CDS is limited to what is contained in the EHR. Second, it is possible that the CDS could erroneously attribute a condition or drug to a patient based on the EHR. In the design phase, the study team will seek and feedback from multiple sources to ensure that the content and CDS firing is as accurate and appropriate as possible. Before implementation, several investigators will review and test the CDS firing to optimize the information displayed. Provider training will inform providers of these limitations and offer strategies to further minimize these risks. Throughout the implementation phase, the study team will request feedback from providers using the CDS to identify any issues and modify the CDS, if needed.

Third, the CDS may be inappropriate for a given individual patient and, if applied without further checking the clinical status of a given patient, could lead to erroneous therapy, adverse events, disability, or death. However, the clinical recommendations are personalized based on the patient's medical problem list, allergies and current medications. The risk of untoward consequences from such clinical actions is considered minimal. Moreover, this potential risk is routinely present in every clinical encounter in the health care system. Fourth, the potential shift in provider prescribing and/or pain management recommendations may also have unintended consequences on patients' post-procedure pain management. It is possible that this shift could cause under-controlled pain. Providers encounter this in current dental practice and will address it in a similar fashion consistent with the reasonable standard of care.

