In addition, patients will receive an educational handout prior to the extraction procedure comparing effectiveness for managing pain, risks and benefits of non-opioid pain medications and opioid medications. This handout intends to initiate a conversation between the patient and provider about patient needs, goals and preferences. The patient will also receive an education handout about pain management after dental extraction for their reference. This handout intends to normalize the experience of some discomfort and to help patients decide about whether to contact their provider for additional help to manage their pain after extraction. Patients will receive usual dental care.

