6.3 MEASURES TO MINIMIZE BIAS: RANDOMIZATION AND BLINDING

The randomization of providers to study arm will utilize stratification on baseline factors in order to balance key provider factors evenly across study arms. Specific stratification factors to be utilized will be outlined in the Statistical Analysis Plan. Providers will be randomly allocated 1:1:1 through a computer-generated program to either Standard Practice, CDS, or CDS-E. Patients will be exposed to the intervention to which their provider has been randomized based on the provider they see at the index extraction visit. Systematic sampling with a variable sampling ratio by provider will be used to identify a sample of patients to receive the post-visit survey. This sampling strategy will approximate stratified random sampling and ensure roughly equal counts of patient surveys by provider and study arm. At each patient encounter, the CDS Web service will collect patient level data from the EHR (e.g., medical conditions, current medications, social history). Providers assigned to the CDS or CDS-E arms will be able to access the information using the CDS tool. Providers assigned to the control arm will continue to use their usual methods to assess and address pain management for dental procedures without any effort to influence their prescribing of analgesics following the dental extraction. They will not be shielded from other outside influences.

At the index encounter (the initial patient visit for a dental extraction during the intervention period where all the study criteria are met), the patient is assigned a unique study identifier that is used to link patient encounter data over time. All index and subsequent encounter data for eligible patients are stored in a limited de-identified analysis dataset.

In order to minimize contamination across study arms, only providers in the CDS or CDS-E arms will be able to access the clinical decision support. Similarly, patients who receive care from providers in the CDS-E arm will have access to supplemental patient education. As such, both groups will know their assignment. The study team will not disclose the study's purpose, objectives, or outcomes measures directly to patients until after the encounter or after the participant has been surveyed about their experience, if selected.

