8.3.4 TIME PERIOD AND FREQUENCY FOR EVENT ASSESSMENT AND FOLLOW-UP

Since there are no routine research contacts for all eligible patient participants, we will collect information from the electronic health record about hospitalizations, emergency department visits, observational bed, and subsequent opioid prescribing made within 3 days post-extraction procedure. This is consistent with the usual care delivery pathways and workflows related to dental procedures.

For the sub-sample of patients reached as part of survey data collection, CESR staff provides information to call their dental provider with questions or concerns. In this manner, the study team will not interfere with existing patient-provider communication, but rather support usual care.

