9.4.4 SAFETY ANALYSES

The study does not include objectives or formal endpoints concerning safety. However, potential harm monitoring activities will be conducted as described in section 8.2, and analysis activities conducted as described below.

Identify whether the CDS inappropriately fires or inappropriately offers considerations

The frequency of notifications and content areas (usability, potential safety, or other) will be summarized by study arm (CDE or CDS-E) and provider type.

Identify potential adverse events

Frequencies, proportions and 95% confidence intervals on proportions of patients having hospitalizations documented in the HealthPartners electronic health record within 72-hours of the extraction encounter deemed as adverse events will be summarized by study arm. The

patient encounter study population for H1 and H2 for patients seen following the implementation of the interventions will be used for this analysis. Events with non-overlapping confidence intervals on the proportions by study arm will prompt the study team to assess diagnostic codes related to the encounters from the electronic health record. Frequencies and proportions of diagnostic codes by study arm will be computed.

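### Harm monitoring counts no unscheduled dental-clinic contacts, so under-controlled pain managed there without a new opioid order goes uncounted, and only hospitalizations are analysed by arm

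*Combined protocol and SAP*

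**What the plan says.** Section 2.3.1 considers what a shift in prescribing might do to patients and states: "It is possible that this shift could cause under-controlled pain". It adds that dental providers already meet this problem and will deal with it as part of ordinary care. Section 8.3.3.3 classes inadequately managed pain as an expected adverse event.

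To identify potential adverse events, Section 8.2 instructs: "Gather hospitalizations, emergency department visits, observational bed, and subsequent opioid prescribing made within 3 days post-extraction procedure". Section 8.3.4 repeats the same four items and the same window. Neither section mentions calls, portal messages or unscheduled return visits to the dental clinic.

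Section 9.4.4 then analyses less than is gathered. It covers "hospitalizations documented in the HealthPartners electronic health record within 72-hours of the extraction encounter deemed as adverse events will be summarized by study arm". Section 7.1 likewise reviews and compares hospitalizations only.

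In the CDS-E arm alone, Section 6.1.1 provides a post-extraction handout, part of whose purpose is "to help patients decide about whether to contact their provider for additional help to manage their pain after extraction". The same handout also aims to present some discomfort as normal.

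On data availability, Section 6.3 says: "All index and subsequent encounter data for eligible patients are stored in a limited de-identified analysis dataset".

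**The concern.** The harm the protocol foresees is pain, and the place it expects pain to be handled is the dental clinic. The harm list consists of hospital-level contacts plus one clinic outcome, a further opioid order. A patient who calls or returns in pain and is managed without an opioid leaves no trace in that list, in any arm. The further opioid order is also an awkward harm marker here, because opioid prescribing is the behaviour the trial sets out to reduce.

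The second issue is comparability. Only CDS-E patients receive written guidance on whether to contact the provider. If that changes where or whether they seek help, the arms could differ in counted events with no difference in uncontrolled pain, or match despite a difference. The DSMB reviews safety by arm (Section 10.1.6) and is consulted on modifying or discontinuing the intervention (Section 7.1), so the gap bears on monitoring as well as on the final report.

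**Working it through.** **1. What is gathered and what is analysed**

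| Event after the extraction | Gathered (8.2, 8.3.4) | Summarised by arm (9.4.4) |
|---|---|---|
| Hospitalization | yes | yes, if deemed an adverse event |
| Emergency department visit | yes | no |
| Observation bed | yes | no |
| Further opioid order | yes | no |
| Dental call, message or return visit for pain, no new opioid order | no | no |

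The core of the point rests on this table and needs no assumption.

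**2. The plan's own figure for the survey**

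Section 9.2 gives 1,520 patients and a 79% response: 1,520 × 0.79 = 1,200.8, which reproduces the stated 1,200. That is about 400 per arm, or 1,200/8,400 = 14% to 1,200/6,900 = 17% of intervention patients.

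Precision for mean pain (the H4 comparison), with 1,200/51 = 23.5 surveys per provider: detectable difference = (1.96 + 0.84) × SD × √(2/n), where n = 400/[1 + 22.5 × ICC]. SD and ICC are assumptions.
- SD 2, ICC 0: n = 400, difference 0.40 points.
- SD 3, ICC 0.10: n = 400/3.25 = 123, difference 1.07 points.

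So mean pain is measured with usable precision, but as a mean in a subsample. It does not count patients with uncontrolled pain or unplanned contacts.

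**3. Illustration of distortion between arms**

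Let p be the true proportion seeking help for pain, and s the share handled at the dental clinic without a new opioid order. The list captures p(1 − s), so the observed CDS-E/SP ratio is p₁(1 − s₁)/[p₀(1 − s₀)]. There are 6,900/3 = 2,300 patients per arm. The documents give neither p nor s; both are assumed.

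| p, SP / CDS-E | s, SP / CDS-E | Captured, SP / CDS-E | True ratio | Observed ratio |
|---|---|---|---|---|
| 5% / 5% | 50% / 50% | 57.5 / 57.5 | 1.0 | 1.00 |
| 5% / 5% | 50% / 70% | 57.5 / 34.5 | 1.0 | 0.60 |
| 5% / 5% | 50% / 40% | 57.5 / 69.0 | 1.0 | 1.20 |
| 5% / 7.5% | 50% / 70% | 57.5 / 51.75 | 1.5 | 0.90 |

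The second and third rows differ only in whether CDS-E patients use the clinic more or less than SP patients. Nothing in the documents settles which.

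**4. Illustration of power**

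Two-proportion normal approximation, two-sided 0.05, for a 1.5-fold rise. Cluster size m = 6,900/51 = 135.3 and design effect = 1 + (m − 1) × ICC. Base rates are assumed.

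Hospitalization at 0.1–0.3% (2,300 × 0.001 = 2.3 to 2,300 × 0.003 = 6.9 events per arm): 7–13% power, ignoring clustering.

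Dental pain contacts at 5–10%:

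| ICC | Design effect | Effective n per arm | Power at 5% / 10% |
|---|---|---|---|
| 0.01 | 2.34 | 982 | 63% / 92% |
| 0.03 | 5.03 | 457 | 35% / 63% |
| 0.10 | 14.4 | 159 | 15% / 27% |
| 0.30 | 41.3 | 56 | 8% / 12% |

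The last row uses the only ICC in the protocol, which is for opioid prescribing and may be too high for pain contacts. The power gain from counting clinic contacts therefore depends on an unknown ICC and is not the reason for the change.

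**The case against.** A reader might infer that the trial fails to see under-controlled pain altogether. The documents do not support that. H4 compares patient-reported pain at days 3–6 in all three arms and does not depend on where a patient seeks help. Later opioid orders pick up clinic contacts that end in one. Section 8.1 also gathers opioid orders and non-opioid recommendations out to 7 days for efficacy. These are partial covers: H4 is descriptive and compares means in 14–17% of patients, Section 9.4.4 does not analyse later opioid orders, and the efficacy endpoints use only the day of extraction.

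A reader might also infer that the gap makes CDS-E look safer than it is. That is not established. The handout addresses whether to call and also normalises discomfort, so contacts could rise or fall. The dental provider is the usual route for pain in every arm. The survey staff's advice ("CESR staff provides information to call their dental provider with questions or concerns") is not restricted to CDS-E either.

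Three further points have weight. The trial states that it has no safety objectives or endpoints. The harm list was widened on the DSMB's recommendation, and the DSMB charter and the Data Safety Monitoring Plan, which could add items, are separate documents, so the omission is shown for the protocol text only. Finally, adding clinic contacts would not remove bias if the handout itself alters readiness to call. None of this explains why the route the protocol expects pain to take is absent from its harm list, or why three of the four items gathered have no planned summary.

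**Conclusion.** The point holds as a gap in harm monitoring that should be closed. Under-controlled pain managed at the dental clinic without a new opioid order is not counted in any arm, and the specified harm analysis covers hospitalizations only. H4 and later opioid orders mitigate this in part.

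Comparisons of acute-care contacts between CDS-E and the other arms may be distorted in either direction. The ratios of 0.60, 0.90 and 1.20 show how far this could go under assumed shares of 40–70% handled at the clinic. They are not estimates. The power figures are equally conditional, ranging from 92% down to 8% with the assumed base rate and ICC.

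**What to change.** In Sections 8.2 and 8.3.4 add, for all arms and over the same window as the other items, unscheduled dental encounters for pain or an analgesic problem recorded in the HealthPartners record: return visits, plus telephone or portal contacts where these are recorded with a reason.

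In Section 9.4.4 summarise these by arm alongside the emergency department, observation-bed and further-opioid items already gathered, each separately and combined as any unplanned pain-related contact. State in advance that:
- CDS versus SP is the cleaner contrast for contacts, because neither arm receives the handout.
- CDS-E differences in contacts will be read together with H4, because the handout may raise or lower the tendency to call.

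The cost is an added event type in a record query already planned, a few more summary rows, and protocol wording. Calls may be incompletely charted or not coded by reason. The documents do not say whether the stored encounter data include calls or messages, so some chart review may be needed. Return visits are the minimum if calls prove unusable. No clinical rule changes.

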7 STUDY INTERVENTION DISCONTINUATION AND PARTICIPANT DISCONTINUATION/WITHDRAWAL

7.1 DISCONTINUATION OF STUDY INTERVENTION

Providers should exercise clinical judgment and can at their discretion disregard any information the CDS offers. As such, patients will receive usual dental care, regardless of study arm.

Hospitalizations documented within the HealthPartners electronic health record that occur within a 72-hour window following the index extraction encounter will be chart reviewed for severity and relatedness on a quarterly basis during the intervention period by Co-investigator and/or PI [name]. These hospitalizations rates will be compared at a frequency determined by the DSMB or quarterly whichever is greater.

Based on the relevant data, the study team in consultation with the DSMB would determine whether the study intervention needed to be modified or discontinued.

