8.3.2 DEFINITION OF SERIOUS ADVERSE EVENTS (SAE)

An adverse event (AE) or suspected adverse reaction is considered "serious" if, in the view of either of the co-PIs, it results in any of the following outcomes: (1) death, (2) a life-threatening adverse event, (3) inpatient hospitalization or prolongation of existing hospitalization, (4) a persistent or significant incapacity or substantial disruption of the ability to conduct normal life functions, or (5) a congenital anomaly/birth defect.

Important medical events that may not result in death, be life-threatening, or require hospitalization may be considered serious when, based upon appropriate medical judgment, they may jeopardize the participant and may require medical or surgical intervention to prevent one of the outcomes listed in this definition.

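### Death is named as a possible harm, but it is missing from the systematic EHR harm capture, the quarterly review and the by-arm harm summary

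*Combined protocol and SAP*

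**What the plan says.** **Where death appears.** Section 2.3.1 says that a display that does not suit the patient, if applied without further checking, "could lead to erroneous therapy, adverse events, disability, or death". Section 8.3.2 defines an adverse event as serious when "it results in any of the following outcomes: (1) death, (2) a life-threatening adverse event" and so on through the list.

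**What is captured.** Section 8.2 sets the EHR procedure for potential adverse events: "Gather hospitalizations, emergency department visits, observational bed, and subsequent opioid prescribing made within 3 days post-extraction procedure". Section 8.3.4 gives the same list and the reason for relying on the record: "Since there are no routine research contacts for all eligible patient participants".

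**What is reviewed and analysed.** Section 7.1 is narrower: "Hospitalizations documented within the HealthPartners electronic health record that occur within a 72-hour window following the index extraction encounter will be chart reviewed". Section 9.4.4 summarises by arm the proportion of "patients having hospitalizations documented in the HealthPartners electronic health record within 72-hours of the extraction encounter deemed as adverse events". Non-overlapping 95% confidence intervals between arms then prompt a look at diagnostic codes.

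**Other routes.** Section 8.3.6 sends serious adverse events to the principal investigator, and 8.4.2 has study team members or clinic staff report unanticipated problems. Sections 8.3.5 and 8.3.6 refer to a separate Data Safety Monitoring Plan for reporting detail. Section 10.1.6 has the DSMB define its data elements at its organizational meeting.

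**The concern.** The EHR pull is the only harm source that covers every patient. It looks for admissions, emergency visits, observation stays and later opioid orders, but not for the most severe outcome that the protocol names. A death with no hospital contact need leave none of those records. In the by-arm table such a patient stays in the denominator with no event, just like a patient who recovered normally.

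What is at stake is the completeness of the harm report. The DSMB is to assess safety data on each arm (10.1.6), and 7.1 bases any decision to modify or discontinue the intervention on the relevant data. A zero for deaths means little if deaths were never looked for. Passive awareness may also differ by arm: 8.2 gives intervention-arm providers training and feedback channels to the study team, and describes none for standard-practice providers. Those channels concern the display, so a difference in death reporting is possible but not shown.

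**Working it through.** The documents give no death rate, death count or safety sample size, so there is no plan figure to reproduce. The main check is textual.

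**1. Is death listed?**

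| Section | Role | Events covered | Window | Death listed? |
|---|---|---|---|---|
| 2.3.1 | Risk statement | Consequences of an inappropriate display | – | Yes |
| 8.3.2 | SAE definition | Serious outcomes | – | Yes, first |
| 8.2 | EHR pull | Hospitalization, emergency visit, observation bed, later opioid prescribing | 3 days | No |
| 8.3.4 | EHR pull | Same four | 3 days | No |
| 7.1 | Quarterly review | Hospitalization | 72 hours | No |
| 9.4.4 | By-arm summary | Hospitalization deemed an adverse event | 72 hours | No |

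**2. How would a death be handled?**

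- No hospital contact: absent from the 8.2 admission and visit items; no event in 9.4.4.
- Death in the emergency department without admission: the visit enters the 8.2 pull, but not 7.1 or 9.4.4.
- Death after admission: counted in 9.4.4 as a hospitalization if deemed an adverse event, not shown as a death.
- Any of these, if staff learn of it: can be reported under 8.3.6 or 8.4.2. Neither section describes a search for deaths or feeds the 9.4.4 table.
- Survey calls: about 1,520 patients are approached (9.2, 9.3), which is 1,520/6,900 = 22% of the target or 1,520/8,400 = 18% of the maximum. A call could reveal a death by chance, but 7.3 classes an unreachable patient as lost to follow-up and mentions no vital-status check.

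**3. What would a systematic count support?**

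Inputs: 6,900 intervention-period patients as target and 8,400 at most (4.1). *Assumption:* equal arms, so 6,900/3 = 2,300 or 8,400/3 = 2,800 per arm. Providers, not patients, are allocated 1:1:1, so actual arm sizes will differ. *Assumption:* every death is ascertained.

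Upper limit with zero deaths:

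- One-sided 95%, one arm: 1 − 0.05^(1/2,300) = 0.130%
- One-sided 95%, both decision-support arms: 1 − 0.05^(1/4,600) = 0.065%
- Two-sided 95% exact, one arm: 1 − 0.025^(1/2,300) = 0.160%; with 2,800, 0.132%

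**4. Would the 9.4.4 trigger work for deaths?**

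The interval method is not stated; exact (Clopper-Pearson) 95% intervals are assumed. For non-overlap, the lower limit in one arm must exceed the upper limit in the other. With 2,300 per arm:

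- Upper limit for 0 deaths: 0.160%
- Lower limit for 8 deaths: 0.150% (overlaps)
- Lower limit for 9 deaths: 0.179% (does not overlap)
- Upper limit for 1 death: 0.242%; lower limit for 11 deaths 0.239% (overlaps), for 12 deaths 0.270% (does not)

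The trigger therefore needs 9 against 0, or 12 against 1. The counts are the same with 2,800 per arm. Wilson intervals would need 8 against 0. An extra table row alone would almost never trigger a review.

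**The case against.** Five points can be made for the plan.

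- **The protocol has other routes.** Sections 8.3.6 and 8.4.2 can bring a death to the investigators, and unanticipated problems that are serious adverse events go to the IRB and the funder within a week. This stands. A reader might infer that a death outside hospital would necessarily go unnoticed, and the documents do not support that. They support only that it would not be systematically sought or counted by arm.
- **Two governing documents were not available.** The Data Safety Monitoring Plan and the DSMB charter may list death. This stands too. A reader might infer that the trial cannot report deaths by arm; the most that can be said is that the protocol does not provide for it.
- **The list was considered.** The amendment history says that 8.2 was expanded to more visit types in line with a DSMB recommendation. That shows that the list was reviewed, but gives no reason for leaving death out.
- **The risk language is generic.** Section 2.3.1 goes on to call the risk minimal and part of any clinical encounter, and the 8.3.2 list is a general definition. The protocol does not predict deaths, and safety is expressly not an objective or endpoint. This limits the severity. It does not explain why less severe events are pulled while death is not.
- **An EHR field may miss out-of-system deaths.** The documents do not say that the record holds vital status or how complete it is. This stands, and it makes the upper limits in the working conditional.

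**Conclusion.** The point holds as a gap in systematic harm capture. Death is in neither EHR pull, nor the quarterly review, nor the by-arm summary, and a patient who died without admission would be counted as event-free in the 9.4.4 table. The text establishes this without any numerical assumption.

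The size is modest. Few or no deaths are expected within 3 days, and no efficacy endpoint or estimate changes. The gain is a harm report that covers the worst outcome the protocol names. The per-arm upper limit of about 0.13% (one-sided, zero deaths, 2,300 patients) may be quoted only as conditional on complete ascertainment and equal arms. If the Data Safety Monitoring Plan or the charter already requires death to be captured, what remains is a cross-reference and a row in the 9.4.4 table. Severity: a minor, low-cost improvement to harm reporting.

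**What to change.** - **8.2 and 8.3.4:** add death from any cause (EHR vital status and date of death, where available) to the pull, over the window already used for the other events.
- **7.1:** add deaths to the data reviewed and compared quarterly.
- **9.4.4:** report deaths by arm regardless of relatedness. Give the DSMB an individual listing as well, without waiting for non-overlapping intervals.
- **Data Safety Monitoring Plan and DSMB charter:** check whether death is already there. If so, cross-refer and align the protocol text.

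The cost is one field in an existing pull, one table row and a short listing. The downside is that out-of-system deaths may be recorded late or not at all. Refresh the field at final extraction, state how complete ascertainment is believed to be, and attach that condition to any upper limit reported. This changes data capture and reporting only; it changes no treatment or clinical rule.
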